1.2 Secondary Objectives

- 1.2.1 Assess the rate of complete remission (CR) / complete remission with incomplete count recovery (CRi) as defined per European Leukemia Net 2017 response criteria at time of count recovery after induction therapy with chemotherapy + Pembrolizumab (MK-3475) (Dohner *et al.*, 2017).
- 1.2.2 Rates of complete remission with partial recovery count (CRh) and Hematologic improvement (HI) to red blood cells and platelets
- 1.2.3 Assess the rates of MRD negativity at Day 14, MRD-negative CR at end of induction therapy and MRD negative CR after last consolidation cycle.
- 1.2.4 Assess event free survival (EFS), measured from randomization to failure to achieve CR/CRi, relapse or death from any cause, and relapse free survival (RFS), calculated as the time from first documentation of CR/CRi to either disease relapse or death from any cause.
- 1.2.5 Assess the duration of response (DOR, defined as the time from first CR/CRi to the date of the first documented relapse or death, whichever occurs first) and overall survival (OS), defined as time from randomization to death from any cause.
- 1.2.6 Assess safety endpoints including proportion of patients who develop severe toxicity as defined in the protocol.

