Follow up: For patients who neither relapse nor die, the DOR will be censored on the date of their last evaluable disease assessment. Median RFS and DOR will be estimated with Kaplan-Meier curves with 95% confidence interval calculated based on the Brookmeyer-Crowley method. Long-term patient survival and disease status information will be collected for up to three years from first dose. An analysis of the survival and RFS data will be conducted based on the five-year follow up from date of randomization. Patients alive at the end of the follow-up period or lost to follow-up will be censored at the last date the patient is known to be alive. Continuous variables will be expressed by means, standard deviations and 95% confidence intervals. Frequencies will be computed for discrete data. Bonferroni's correction will be used for multiple comparisons, if any, to protect the overall type I error rate.

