10.4 Analysis of Secondary and Exploratory Endpoints

10.4.1 Secondary Endpoints

10.4.1.1 Efficacy Endpoints:

- Assess the rate of CR/CRi as defined per the ELN 2017 (see Appendix D) response criteria at time of count recovery after induction therapy with chemotherapy + Pembrolizumab (MK-3475).
- Assess MRD negativity at Day 14.
- Assess the rate of MRD-negative CR at end of induction therapy.
- Assess the rate of MRD-negative CR at end of consolidation.
- Assess rates of complete remission with partial recovery count (CRh) and Hematologic improvement (HI) to red blood cells and platelets.
- Assess the percentage of patients with MRD-CR at time of count recovery after first cycle of consolidation therapy using a MRD cut-off of 0.01%.
- Assess EFS, RFS, calculated as the time from initial treatment to either disease relapse or death.
- Assess the DOR (defined as the time from first CR to the date of the first documented relapse or death, whichever occurs first) and OS.

10.4.1.2 Safety Endpoints:

- Assess safety endpoints including proportion of patients who develop severe toxicity.

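### Section 10.1 appears to censor RFS at the last date known alive, which counts unassessed time as relapse-free, and the protocol gives RFS two different start dates

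*Combined protocol and SAP*

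**What the plan says.** **Censoring (Section 10.1, follow-up paragraph).** DOR has its own rule: "For patients who neither relapse nor die, the DOR will be censored on the date of their last evaluable disease assessment". RFS and DOR medians are then both to be estimated by Kaplan-Meier. Next comes "An analysis of the survival and RFS data will be conducted based on the five-year follow up from date of randomization", and directly after it the rule that patients alive at the end of follow-up or "lost to follow-up will be censored at the last date the patient is known to be alive". No sentence gives a censoring rule for RFS by name.

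**Definitions.**
- Section 1.2.4 has "relapse free survival (RFS), calculated as the time from first documentation of CR/CRi to either disease relapse or death from any cause". Section 1.2.5 has DOR "defined as the time from first CR/CRi to the date of the first documented relapse or death, whichever occurs first". There the two share the same start and the same events.
- Section 10.4.1.1 has "Assess EFS, RFS, calculated as the time from initial treatment to either disease relapse or death", while DOR is "defined as the time from first CR to the date of the first documented relapse or death, whichever occurs first".
- Section 13.3 repeats the initial-treatment start for RFS, gives EFS and RFS a single definition, and starts DOR at first CR.

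**The concern.** A last-known-alive date tells us about death and nothing about relapse. If a responder's marrows and counts stop but a later contact shows the patient alive, censoring RFS at that contact keeps the patient in the risk set as relapse-free through a period nobody examined. Relapses in that period are missed, or are recorded only as later deaths, and the RFS curve sits too high.

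Several provisions allow the two dates to separate:
- The three-monthly maintenance marrows are optional in the Section 5.1 table and in footnote p of the study calendar, although Section 7.1.3 describes them as planned.
- Section 7.1.3 follows transplanted patients for survival and serious adverse events over the first 100 days. That sentence does not mention disease status.
- Section 10.1 collects survival and disease status for up to three years from first dose, yet bases the RFS analysis on five years from randomization. Footnote c of the calendar follows survival to three years after end of treatment.

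The unsettled start date compounds this. Under Section 1.2 RFS is a responders-only quantity identical to DOR. Under Sections 10.4.1.1 and 13.3 it runs from initial treatment and cannot be told apart from EFS.

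**Working it through.** **The plan's own figures.** No RFS or DOR median, rate, event count or power is stated, so there is nothing to reproduce for these endpoints. The only design power is for the primary endpoint, 50% vs 75% with 25 per arm and one-sided alpha 0.1:
- null SE = √(2 × 0.625 × 0.375 / 25) = 0.1369
- alternative SE = √(0.25/25 + 0.1875/25) = 0.1323
- power = Φ[(0.25 − 1.2816 × 0.1369) / 0.1323] = Φ(0.563) = 0.713

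This matches the stated 71% or so, and nothing below bears on it.

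**Simulation inputs (all assumed).**
- True RFS from remission is exponential with median m = 12, 18 or 24 months.
- 85% of first events are relapses: relapse hazard 0.85 × ln2/m, death-in-remission hazard 0.15 × ln2/m.
- Median survival after relapse is 8 months.
- A share q of 10-30% of responders stops disease assessment at a uniform time in months 0-24; the rest are assessed to month 60.
- After assessment stops, vital status stays known for 6 months, 12 months or to month 60.
- 200,000 patients per scenario.

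**Rules compared.**
- A: censor at last date known alive.
- B: censor at last assessment, but still count a later known death as an event. The DOR sentence as written can be applied this way, because it censors only patients who neither relapse nor die.

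**Medians in months, ranges over q = 10-30%.**

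| True | A, all follow-up lengths | B, vital status 6-12 months longer | B, vital status to month 60 |
|---|---|---|---|
| 12 | 12.3-12.8 | 11.9-12.0 | 12.3-12.7 |
| 18 | 18.3-19.5 | 17.3-17.9 | 18.3-18.8 |
| 24 | 24.5-26.1 | 22.8-24.0 | 24.4-24.5 |

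- Rule A, median: smallest excess 18.3/18 = 1.017, largest 26.1/24 = 1.088, so about 2-9% too high.
- Rule A, 24-month RFS: 25.6-28.6% against 25.0%; 40.4-43.0% against 39.7%; 50.8-52.8% against 50.0%. The excess is 0.6 to 3.6 points.
- Rule B, median: 22.8/24 = 0.95 to 12.7/12 = 1.06, so −5% to +6%.
- With q = 0 the two rules give the same result. The largest gap between them is 25.8 − 22.8 = 3.0 months (true median 24, q = 30%, vital status 12 months longer).

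**Second set of assumptions.** Median time to relapse is 14 months, death in remission occurs at 10% of the relapse rate, median survival after relapse is 12 months, and q = 10-40%. True 24-month RFS is 0.5^(24 × 1.1/14) = 27%. Rule A gives 28.5% to about 33%. Rule B gives 24-32%, depending on q and data cut-off. Censoring at the last assessment and disregarding deaths after it gives 27%. That last result is expected, because stopping was simulated as independent of relapse; it would not be guaranteed if patients stop because they are failing.

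**The case against.** **The sentence never says RFS.** It uses standard OS wording, and an OS-only reading is possible. This stands: applying it to RFS is an inference. But on the OS-only reading RFS has no censoring rule of its own, and the choice is left open in an open-label trial. One could argue that RFS should borrow the DOR rule, since the paragraph treats both medians together; that would also need to be written down.

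**Disease follow-up is planned alongside survival.** Section 7.4 collects survival and remission status together at least every six months for up to five years. Section 10.1 also pairs them, Section 7.3 continues marrow and blood assessments through dosing interruptions, and blood sampling in maintenance stays mandatory. This also stands. It limits the gap, though the provisions listed above mean it does not exclude one. A reader might infer that RFS will be overstated; the documents support only that it will be if survival contact outlasts disease assessment.

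**The effect is small beside sampling error.** Assuming 35 responders (70% of 50), the SE of a 27% RFS estimate is √(0.27 × 0.73/35) = 7.5 points. That is fair. The case rests on an unsuitable and ambiguous prespecified rule, and no between-arm bias has been shown.

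**RFS and DOR are not simply duplicates.** From Section 1.2 alone a reader might conclude that one quantity is being reported twice and that DOR should go. Sections 10.4.1.1 and 13.3 define different quantities, so differing medians would be expected there. Dropping DOR, or replacing it with cumulative incidence of relapse, is a preference and not a correction.

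**Conclusion.** The point holds in a conditional form. Read naturally, Section 10.1 censors RFS at a date suited to OS, which biases RFS upward to the extent that survival contact continues after disease assessment has stopped. Under the assumed scenarios in which 10-30% of responders stop assessment early, that means about 2-9% on the median and 0.6-3.6 points at 24 months. It is zero when the dates coincide, and the documents cannot say where in that range the trial will fall. Switching to last-assessment censoring is not enough by itself, because counting later deaths as events leaves an error of −5% to +6% on the median.

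Independently of censoring, RFS has two incompatible start dates, one making it identical to DOR and the other merging it with EFS. That conflict is plain on the page and needs no assumptions. Both problems concern secondary endpoints. They should be corrected before analysis.

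**What to change.** 1. **One RFS definition.** In Sections 1.2.4, 10.4.1.1 and 13.3, start RFS at first documented CR/CRi, with relapse or death as events, and define EFS separately.
2. **Censoring by endpoint in Section 10.1.** Suggested wording: *EFS, RFS and DOR are censored at the last evaluable disease assessment without an event. Censoring at the last date known alive applies to OS only.*
3. **Deaths after assessment has stopped.** State the handling, for example censoring at the last assessment before the gap, with a sensitivity analysis that counts the death as an event.

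The follow-up lengths in Section 7.4, Section 10.1 and calendar footnote c should be reconciled at the same time, because a five-year RFS analysis needs disease status collected for as long.

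The cost is a few sentences and one sensitivity analysis. Reported RFS may become slightly less favourable. The primary endpoint, power and sample size do not change.

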10.1.1 Primary endpoint

MRD-negative CR/CRi response rate at time of count recovery after first cycle of consolidation therapy with chemotherapy + Pembrolizumab (MK-3475) vs. 7+3 and one cycle of consolidation chemotherapy alone.

10.1.2 MRD assessment by multicolor flow cytometry (MFC) as an integral biomarker

The current state of the art in AML MRD by flow cytometry can detect 0.1% for ~95% of patients and 0.01% for a major subset of those (~40-50%) but is heavily dependent on the immunophenotype of the leukemia and nature of the background population. The sensitivity of the assay varies depending on those two variables, so the threshold at present is not uniformly

0.01% for all patients. Importantly, the primary fertility and efficacy analyses will compare MRD negative CR/CRi rates between the two arms, and if the MRD by flow can detect below this limit of 0.01% in only 40% of patients, then 60% of patients might not contribute to study primary endpoint differential effect. Given the limitations of the current technology, an MRD quantified below <0.1% may still be consistent with residual leukemia. We therefore have decided to use this cutoff to distinguish MRD-positive from MRD-negative patients as this threshold was found relevant in most published studies to date and has been included in the official consensus document on minimal residual disease by the European Leukemia Net MRD Working Party. Thus, cutoff levels below 0.1% (e.g., <0.01%) may define patients with particularly good outcome.

10.2 Sample Size/Accrual Rate

A total of 50 patients (25 per arm) are planned to be enrolled in the intent-to-treat analysis, which will evaluate a 25% difference in the rate of MRD-negative CR/CRi with ~71% power and an overall, one-sided alpha level of 0.1. All patients being randomized and starting induction therapy should be included in the primary analysis.

PLANNED ENROLLMENT REPORT

Racial Categories	Ethnic Categories				Total
	Not Hispanic or Latino		Hispanic or Latino		
	Female	Male	Female	Male	
American Indian/ Alaska Native	0	0	0	0	0
Asian	1	1	0	0	2
Native Hawaiian or Other Pacific Islander	1	1	0	0	2
Black or African American	1	1	1	1	4
White	15	20	1	2	38
More Than One Race	1	1	1	1	4
Total	19	24	3	4	50

10.3 Stratification Factors

Planned stratification factors include age (younger than 65 vs. 65 and older), cytogenetics by FISH or metaphase karyotype (presence vs. absence of core binding factor inversions and translocations), and t-AML or AML arising from prior/antecedent MDS (yes/no). Dose escalation and MTD determination are not parts of this study.

10.4 Analysis of Secondary and Exploratory Endpoints

10.4.1 Secondary Endpoints

10.4.1.1 Efficacy Endpoints:

- Assess the rate of CR/CRi as defined per the ELN 2017 (see Appendix D) response criteria at time of count recovery after induction therapy with chemotherapy + Pembrolizumab (MK-3475).
- Assess MRD negativity at Day 14.
- Assess the rate of MRD-negative CR at end of induction therapy.
- Assess the rate of MRD-negative CR at end of consolidation.
- Assess rates of complete remission with partial recovery count (CRh) and Hematologic improvement (HI) to red blood cells and platelets.
- Assess the percentage of patients with MRD-CR at time of count recovery after first cycle of consolidation therapy using a MRD cut-off of 0.01%.
- Assess EFS, RFS, calculated as the time from initial treatment to either disease relapse or death.
- Assess the DOR (defined as the time from first CR to the date of the first documented relapse or death, whichever occurs first) and OS.

10.4.1.2 Safety Endpoints:

- Assess safety endpoints including proportion of patients who develop severe toxicity.

10.4.2 Exploratory Endpoints

10.4.2.1 MRD assessment by DS as an exploratory biomarker

All diagnostic and remission samples will undergo DNA extraction at the Fred Hutchinson

Cancer Research Center. De-identified DNA samples will be shipped to TwinStrand for DS at an average molecular depth of 20,000x. Samples will initially be investigator-blinded as to any patient information. Library preparation, sequencing, and analysis will be performed with TwinStrand's optimized workflow, and TwinStrand's bioinformatics core will perform all analyses related to assay output.

We anticipate two potential issues using DS:

(1) MRD positive cases without relapse ("false positives"):

It is possible that our assay will not always be able to distinguish true MRD from clonal hematopoiesis of indeterminate potential (CHIP), and misclassification of CHIP as MRD would yield "false positive" results. While some mutations in AML genes (*e.g.*, *KRAS*, *FLT3*) are pathognomonic for disease, others (*e.g.*, *DNMT3A*) are potentially related to CHIP and can persist in remission without indicating imminent relapse and can even be detected in healthy older individuals. Rather than simply ignoring these mutations, we will use our dataset to see if they can provide prognostic information. If our model does not adequately differentiate between MRD and CHIP based on a high proportion of false positive cases, we will consider alternative strategies, including having our Fred Hutch collaborators perform flow sorting to isolate lymphoid cells, with the theory that mutations present in both lymphoid and myeloid cells are very likely to be CHIP-related.

It should be noted that any sufficiently sensitive MRD assay faces with the same problem of distinguishing biological background from true disease, and this issue is not unique to our novel DS approach. Rather than ignoring the "CHIP problem", however, we will harness the power of a large dataset plus the unprecedented sensitivity of the DS platform to understand how best to analyze all genomic data, CHIP-related and not, to provide prognostic information.

(2) MRD negative cases that relapse ("false negatives"):

One reason for residual disease to be undetectable in bone marrow is hemodilution, or contamination with peripheral blood. We will verify whether hemodilution is present on pathology reports. However, we should also consider the possibility that our assay either does not capture or is insufficiently sensitive for the particular persistent clone(s).

Insufficient quantity of DNA is unlikely to lead to false negatives: ~1 µg is needed for DS, and we would expect to isolate dozens of micrograms from each sample. In all "false negative" cases, we will perform our DS panel on the patient's marrow sample from diagnosis. For any mutations present at diagnosis, we would plan to repeat sequencing to a greater depth on remission marrows just for this subset. Practically, we would be able to sequence to a depth of 50,000x or 100,000x, which would provide 80% power to detect alleles with frequency of 0.003% (1 in 30,000) or 0.0017% (1 in 60,000) respectively. While we have designed our panel to have one-size-fits-all utility for the vast majority of AML patients, if we find that deeper sequencing reduces false negatives, we could either routinely sequence the entire panel more deeply or, most cost-effectively, simply use only a small subset of the probes to interrogate mutations known to be relevant for a given patient based on diagnosis. It is also possible that rare patients will have mutations that are not picked up in our panel. Our panel, which is relatively small,

does not include several larger AML-associated rearrangements. Many commercial products based on RT-PCR are able to detect these rearrangements extremely accurately. For the rare samples where these are the only markers of disease, we could supplement our panel with specific RT-PCR for these fusion products.

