The [name] Lab is working with TwinStrand (a University of Washington “spin off”) to use DS to sequence mutations in acute and chronic leukemia (Araki *et al.*, 2016). This team has carefully selected a panel of 25 genes with the most common point mutations, insertions, deletions, fusions, and duplications associated with AML. They have developed probes targeting whole genes (*e.g.*, *RUNX1*, *TP53*, *etc.*) or specific mutational hotspots (*e.g.*, *FLT3* point mutations and internal tandem duplications (ITD), *NPM1* insertions, *etc.*). These genes are covered by a ~40 kilobase (kb) panel which comprises a median of 99% of all AML-associated mutations within the selected genes. A ~30 kb panel of genes will be used. Sequencing to a depth of 20,000x is expected to provide a 98% power to detect an allele frequency of 0.02% (1 in 5000) and 86% power to detect alleles at 0.01% frequency (see Figure 2, below).

Patients with AML will have DS performed on the bone marrow (BM) and PB at the time of study entry,

at Day 14, at the end of induction therapy (EOI), after one cycle of consolidation therapy, and at the end of consolidation therapy (EOC), and at end of maintenance therapy/observation period for patients who do not progress. For patients who are willing to have BM done every 3 months during follow up, DS in BM and PB could be assessed during maintenance therapy/observation period.

Figure 2. Sensitivity of Duplex Sequencing is a function of input DNA quantity and sequencing depth. Low-level mutations can be detected reliably at 20,000x based on statistical modeling

(Unpublished Data).

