10.4.2.1.1 Comparing DS and MFC for MRD detection as an exploratory biomarker

In order to compare both approaches, DS will be performed on these samples at a molecular depth of 20,000x and at the same time the samples will also perform 10-color MFC, although researchers will be blinded to MFC results. The primary analysis will involve comparison in performance of MRD detected by DS vs. MFC patients. McNemar's Chi-squared test for paired samples (regular DS vs. MFC and ultra-deep DS vs. MFC) will be used to compare the MRD measures.

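### Ultra-deep sequencing is planned only for DS-negative patients who later relapse, so the named McNemar comparison of ultra-deep DS with flow cytometry is not valid

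*Combined protocol and SAP*

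**What the plan says.** Section 10.4.2.1 sets one depth for all diagnostic and remission samples: "De-identified DNA samples will be shipped to TwinStrand for DS at an average molecular depth of 20,000x". It then lists two anticipated problems. The second is false negatives, defined by outcome as "MRD negative cases that relapse".

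For these patients the first step reads "cases, we will perform our DS panel on the patient's marrow sample from diagnosis". Where a mutation was present at diagnosis, the remission marrow is sequenced again: "we would plan to repeat sequencing to a greater depth on remission marrows just for this subset". On depth the text says "we would be able to sequence to a depth of 50,000x or 100,000x", with a stated "80% power to detect alleles with frequency of 0.003% (1 in 30,000) or 0.0017% (1 in 60,000) respectively".

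If the retest reduces false negatives, the plan mentions two later options: sequencing the whole panel more deeply as routine, or using a small patient-specific set of probes.

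Section 10.4.2.1.1 describes the DS and MFC analysis as a comparison of performance. It specifies McNemar's chi-squared test for paired samples, with the pairs given as "regular DS vs. MFC and ultra-deep DS vs. MFC) will be used to compare the MRD measures". It does not say which samples form the ultra-deep set, or whether a deeper call replaces the 20,000x call.

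**The concern.** A paired test of two assays needs both applied to the same patients, chosen without regard to the outcome used to judge them. Here the retest in Section 10.4.2.1 is the only planned source of ultra-deep data, and later relapse triggers it. No DS-negative patient who stays in remission, no DS-positive patient and no random sample is scheduled for it. Relapsers missed by MFC get no matching second look.

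The plan itself warns that clonal hematopoiesis (CHIP) can make DS positive without relapse. That is the cost greater depth might bring, and a retest confined to relapsers cannot show it. At stake are the ultra-deep comparison and any later choice of assay depth that leans on it. The flow-based primary endpoint and its power are not involved.

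**Working it through.** **1. The plan's detection figures.** The chance of at least one mutant molecule at depth d and allele frequency f is 1 - (1 - f)^d.

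- 20,000x (Section 2.5.2 states "98% power to detect an allele frequency of 0.02% (1 in 5000) and 86% power to detect alleles at 0.01% frequency"): 98.2% at 0.02% and 86.5% at 0.01%. Both reproduce.
- 50,000x at 1 in 30,000: 81.1%. 100,000x at 1 in 60,000: 81.1%. Both agree with the stated 80%. The rounded percentages give 77.7% at 0.003% and 81.7% at 0.0017%.

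The same formula at 20,000x gives 1 - (1 - 1/30,000)^20,000 = 48.7% and 1 - (1 - 1/60,000)^20,000 = 28.3%. Depth therefore matters greatly to whether a low-level clone is called positive.

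**2. Who gets which depth.**

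| Remission sample | 20,000x | Ultra-deep |
|---|---|---|
| DS-positive | yes | not planned |
| DS-negative, no relapse | yes | not planned |
| DS-negative, relapse, no panel mutation at diagnosis | yes | not planned |
| DS-negative, relapse, panel mutation at diagnosis | yes | planned |

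The documents leave two possible analysis sets.

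**3. Set A: only retested cases.** All are relapsers, so there are no non-relapsers from whom to estimate specificity. All were DS-negative at 20,000x by selection, while MFC was not selected on.

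The expected number is N x relapse rate x (1 - Se), before the mutation-at-diagnosis requirement reduces it further. Assuming 25 to 45 patients in remission, 30% to 50% relapse and DS sensitivity 0.5 to 0.8, this runs from 25 x 0.30 x 0.20 = 1.5 to 45 x 0.50 x 0.50 = 11.25. With five discordant pairs the smallest two-sided exact McNemar p-value is 2 x 0.5^5 = 0.0625. The uncorrected chi-squared statistic for five pairs in one direction is 25/5 = 5.0, above 3.84, so the chi-squared form is unreliable at these counts.

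**4. Set B: retested calls merged with the 20,000x calls.** Let q be the proportion of all DS-negative relapsers whose call turns positive. If calls are scored against relapse, recorded sensitivity = Se + (1 - Se)q and recorded specificity = Sp. The recorded gain in Youden index is (1 - Se)q, which is never negative.

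Had all DS-negative samples been retested, with a proportion r of DS-negative non-relapsers converting, specificity would be Sp(1 - r). The Youden gain would vanish at r = (1 - Se)q/Sp. The documents give no Se, Sp, q or r. Assuming Se 0.60, Sp 0.80 (Youden 0.40) and 40% relapse:

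| q | Sensitivity | Recorded specificity | Recorded Youden | Recorded accuracy gain, 0.40 x 0.40 x q | r at which the true Youden gain is zero |
|---|---|---|---|---|---|
| 0.1 | 0.64 | 0.80 | 0.44 | 1.6 points | 0.05 |
| 0.2 | 0.68 | 0.80 | 0.48 | 3.2 points | 0.10 |
| 0.5 | 0.80 | 0.80 | 0.60 | 8.0 points | 0.25 |

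The recorded columns are the same whatever r is. Over assumed Se 0.5-0.8 and q 0.1-0.5 the recorded Youden gain runs from 0.20 x 0.1 = 0.02 to 0.50 x 0.5 = 0.25.

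The extreme case is a retest that carries no information (r = q). Retesting every negative would then give specificity 0.72, 0.64 and 0.40 and Youden 0.36, 0.32 and 0.20, a loss each time. Under the relapse-triggered rule the same useless retest still records a gain.

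**5. Raw positivity, which is what McNemar's test compares.** In set B, ultra-deep DS has at least as many positives as regular DS, but no more than if every sample had been sequenced deeply. In set A, selecting DS-negatives may work against DS if deep and regular calls are correlated. The direction of bias is therefore not fixed.

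**The case against.** The strongest reply is that McNemar's test on paired calls compares positivity rates. Section 10.4.2.1.1 names no sensitivity, specificity or relapse standard, and the relapse-prediction models in Section 10.4.2.1.2 do not mention ultra-deep calls. That stands, and it limits the claim. A reader might infer that the McNemar result must favour ultra-deep DS. The documents do not support this: inflation follows only if merged calls are scored against relapse, and step 5 shows that the raw direction is open.

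A reader might also infer that deeper sequencing would sharply reduce specificity. The documents do not support this either. The equal-conversion case is an extreme: Section 2.5.2 gives a DS error rate below 1 per 10 million base pairs, so sequencing error would not produce it. Persistent CHIP could convert some non-relapsers, but no rate is given.

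Nor is it certain that non-relapsing DS-negatives will never be sequenced deeply, since routine deeper sequencing is a later option. It is conditional on a retest that can only reduce false negatives.

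The word subset may refer to mutations rather than patients. The paragraph still applies only to DS-negative patients who relapsed, so selection on outcome remains. Blinding does not help: Section 10.4.2.1 blinds investigators only initially, and Section 10.4.2.1.1 blinds to MFC. Neither covers a retest that relapse sets off.

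Finally, looking again at missed relapses is a legitimate root-cause check, and the wording is tentative. That is fair. The problem is the separate step of naming the result as a paired comparison with MFC.

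**Conclusion.** The concern holds in a limited form. The ultra-deep DS versus MFC comparison is not valid as planned, because the only ultra-deep data come from patients selected on relapse. One possible analysis set cannot estimate specificity; the other makes sequencing depth depend on the outcome. This rests on the text alone, specifically on Section 10.4.2.1 being the only planned source of ultra-deep calls.

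That accuracy scored against relapse can only improve follows from the algebra. How much it improves does not: a Youden gain of 0.02 to 0.25 is an illustration over assumed sensitivities and conversion rates. No direction is claimed for raw McNemar positivity. The 20,000x DS versus MFC comparison is not affected by the retest. The consequence is confined to an exploratory biomarker analysis, so this is a low-priority correction.

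**What to change.** In Section 10.4.2.1.1, delete ultra-deep DS from the McNemar comparison and keep DS at 20,000x against MFC. In Section 10.4.2.1, state that the relapse-triggered retest is a descriptive root-cause check: report how many cases were eligible, how many were retested and how many turned positive, without accuracy estimates and without replacing the 20,000x calls. This is a wording change with no new data.

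Only if the ultra-deep comparison is wanted, sequence all DS-negative remission samples to the same depth, or a sample of them drawn without knowledge of relapse. Keep the laboratory blinded to relapse and MFC, and state which samples enter and which call is used. Base any change of routine depth on those data. The cost is extra sequencing of stored DNA. The plan expects dozens of micrograms per sample against about 1 µg needed, so material should not be the limit.
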